## **3.3 Efficacy Analysis**

### **3.3.1 General consideration for efficacy analysis**

#### Analysis population

All efficacy endpoints will be evaluated in the ITT and per-protocol population as defined in Section 3.1.

The analyses performed in the per-protocol population will be considered the primary analyses, and the analyses based on ITT population will be considered as sensitivity analyses.

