5.6. Study Rationale

A biological effect of BIIB033 was shown in Study 215ON201 in subjects with AON. In this study, subjects received 6 doses of 100 mg/kg BIIB033 or placebo administered via IV infusion every 4 weeks up to Week 20, with Follow-Up Visits at Weeks 24 and 32. Efficacy results showed an improvement in mean change in full-field visual evoked potential (FF-VEP) latency values of the affected eye from the baseline of the fellow eye at Week 24 in the BIIB033 group compared with placebo in the intent-to-treat population (-3.48 [95% confidence interval (CI): -10.61, 3.65] msec, analysis of covariance [ANCOVA]). The treatment effect was more pronounced in the per-protocol population (-7.55 [95% CI: -15.12, 0.01] msec, ANCOVA). The electrophysiologic differences between the treatment and placebo groups, first observed at Week 12 during the dosing period, persisted throughout the subsequent monthly dosing visits.

The change in FF-VEP latency in the affected eye versus the baseline of the unaffected fellow eye by mixed model for repeated measures (MMRM) showed a greater treatment effect at Week 32 than at Week 24 for both the intent-to-treat (ITT) and per-protocol populations, despite subjects completing the dosing period at Week 20. In the ITT population, an improvement of -6.06 msec over placebo was seen in the BIIB033 group at Week 32 by MMRM ($p = 0.0711$). A significant improvement of -9.13 msec over placebo was seen in the BIIB033 group at Week 32 in the per-protocol population by MMRM ($p = 0.0112$).

Study 215ON201 also showed that all subjects, regardless of assigned treatment, recovered clinically to a large extent regardless of treatment assignment or severity of injury to the retina or the optic nerve; however, not all subjects demonstrated complete functional recovery upon electrophysiologic examination. The rationale for the discrepancy between clinical recovery and electrophysiological improvement is unclear and requires further investigation.

Given these data, the proposed follow-up study is necessary to assess the long-term electrophysiologic and clinical outcomes of this patient population with past randomized exposure to remyelinating therapy versus placebo, but also to explore potential mechanism(s) by which patients recover from previous AON. This information will be critical in the ongoing clinical development of remyelinating therapies so that they can be optimally evaluated and utilized for maximal benefit.

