14.1. Efficacy

14.1.1. Analysis Population

Analysis of efficacy endpoints will be based on all enrolled subjects who complete the 1-day assessments.

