5.6. Study Rationale

A biological effect of BIIB033 was shown in Study 215ON201 in subjects with AON. In this study, subjects received 6 doses of 100 mg/kg BIIB033 or placebo administered via IV infusion every 4 weeks up to Week 20, with Follow-Up Visits at Weeks 24 and 32. Efficacy results showed an improvement in mean change in full-field visual evoked potential (FF-VEP) latency values of the affected eye from the baseline of the fellow eye at Week 24 in the BIIB033 group compared with placebo in the intent-to-treat population (-3.48 [95% confidence interval (CI): -10.61, 3.65] msec, analysis of covariance [ANCOVA]). The treatment effect was more pronounced in the per-protocol population (-7.55 [95% CI: -15.12, 0.01] msec, ANCOVA). The electrophysiologic differences between the treatment and placebo groups, first observed at Week 12 during the dosing period, persisted throughout the subsequent monthly dosing visits.

The change in FF-VEP latency in the affected eye versus the baseline of the unaffected fellow eye by mixed model for repeated measures (MMRM) showed a greater treatment effect at Week 32 than at Week 24 for both the intent-to-treat (ITT) and per-protocol populations, despite subjects completing the dosing period at Week 20. In the ITT population, an improvement of -6.06 msec over placebo was seen in the BIIB033 group at Week 32 by MMRM ($p = 0.0711$). A significant improvement of -9.13 msec over placebo was seen in the BIIB033 group at Week 32 in the per-protocol population by MMRM ($p = 0.0112$).

Study 215ON201 also showed that all subjects, regardless of assigned treatment, recovered clinically to a large extent regardless of treatment assignment or severity of injury to the retina or the optic nerve; however, not all subjects demonstrated complete functional recovery upon electrophysiologic examination. The rationale for the discrepancy between clinical recovery and electrophysiological improvement is unclear and requires further investigation.

Given these data, the proposed follow-up study is necessary to assess the long-term electrophysiologic and clinical outcomes of this patient population with past randomized exposure to remyelinating therapy versus placebo, but also to explore potential mechanism(s) by which patients recover from previous AON. This information will be critical in the ongoing clinical development of remyelinating therapies so that they can be optimally evaluated and utilized for maximal benefit.

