#### Analysis population

Intent-to-treat (ITT) population, per-protocol population, and safety population are defined as follows.

- *Intent-to-Treat Population*

The intent-to-treat population is defined as all randomized subjects who received at least 1 dose of study treatment (BIIB033 or placebo) in 215ON201 study, and completed at least one of the 1-day assessments in this study.

- *Per-protocol Population*

The per-protocol population is defined as subjects from the ITT population who completed the 215ON201 study, did not miss more than one dose of BIIB033 or placebo, and did not receive MS modifying therapies during study 215ON201. These subjects were included in the per-protocol population of 215ON201 study.

- *Safety population*

The safety population is defined as all subjects who received at least 1 dose of study treatment in 215ON201 and completed at least one of the 1-day assessments in this study.

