### **3.2.2 Accounting of Subjects**

The summary of subjects disposition will include: subjects who completed the study; and subjects who withdrew from study early and the reasons for withdrawal. A listing of those subjects who withdrew from study and the associated reasons for withdrawal will be presented by treatment group. Number of subjects in each analysis population defined in Section 3.1 will also be summarized.

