### **3.3.2 Primary Efficacy Endpoint**

In order to be included in the statistical analyses of the FF-VEP data the subject had to have been evaluated using the same monitor type in both the 215ON201 and 215ON203 studies.

Subjects who were evaluated using different monitor types will have their FF-VEP data excluded from the statistical analyses. These data will appear in the subject listings.

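### The SAP makes the per-protocol set primary and ITT a sensitivity analysis, against Protocol 14.1.1 and without a stated reason, leaving the headline result open to selection bias

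*SAP*

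**What the plan says.** SAP 3.3.1 (Analysis population) evaluates every efficacy endpoint in both the ITT and the per-protocol populations, then ranks them: "The analyses performed in the per-protocol population will be considered the primary analyses", with the ITT analyses as sensitivity analyses.

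SAP 3.1 takes the per-protocol set from ITT subjects who completed 215ON201, "did not miss more than one dose of BIIB033 or placebo, and did not receive MS modifying therapies during study 215ON201". It adds: "These subjects were included in the per-protocol population of 215ON201 study". ITT there means randomised subjects who received at least one dose in 215ON201 and completed at least one of the assessments in this study.

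Protocol 14.1.1 says: "Analysis of efficacy endpoints will be based on all enrolled subjects who complete the 1-day assessments". It defines no per-protocol set for 215ON203. The wording is the same in version 4.0 and in version 3.0, whose +4-month visit window the SAP uses.

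Two further provisions matter. SAP 3.3.2 says: "Subjects who were evaluated using different monitor types will have their FF-VEP data excluded from the statistical analyses". On accounting, SAP 3.2.2 says: "Number of subjects in each analysis population defined in Section 3.1 will also be summarized".

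**The concern.** The analysis labelled primary is not the one the protocol specifies, and it gives up part of the randomised comparison on which the study's rationale rests. Completing the parent study, missing no more than one dose and staying off MS-modifying therapy are all post-randomisation events. They can differ between arms for reasons linked to outcome.

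The documents suggest how. Protocol 5.5.2 reports two BIIB033 subjects with serious hypersensitivity reactions during infusion in 215ON201, and says that infusions were stopped in all hypersensitivity cases. If doses were then missed, those exclusions would fall on one arm; the documents do not say whether this happened. For time to CDMS, which SAP 3.3.3 counts from the diagnosis of optic neuritis, dropping subjects who took MS-modifying therapy during 215ON201 may remove some early converters, which is selection on the outcome itself.

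The choice also runs in a direction already known to favour BIIB033. Protocol 5.6 says of Week 24: "The treatment effect was more pronounced in the per-protocol population". The FF-VEP comparison is most exposed, both at the end and at the interim (SAP 4), which is meant to inform ongoing development.

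**Working it through.** **Order of events.** Section 5.6 of Protocol version 1.0 already prints the parent results by population, including: "A significant improvement of -9.13 msec over placebo was seen in the BIIB033 group at Week 32 in the per-protocol population by MMRM". The SAP is later than version 1.0, because it lists SDMT as a secondary endpoint and version 1.0 does not. So the per-protocol set was given primary status after its larger effect was known. Version lag does not explain the conflict, since 14.1.1 reads the same in versions 3.0 and 4.0.

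**Parent figures (Protocol 5.6).** The documents contain no sample size calculation or per-protocol count to reproduce, so the check is on the parent results.

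Week 24, ANCOVA. SE = half-width / t(0.975); the analysed n is not given, so df 79 (n = 82) is assumed, with t = 1.990.
- ITT: -3.48 (95% CI -10.61 to 3.65). Half-width (3.65 + 10.61)/2 = 7.13; SE = 3.58; t = 3.48/3.58 = 0.97; p about 0.33.
- Per-protocol: -7.55 (-15.12 to 0.01). Half-width (0.01 + 15.12)/2 = 7.565; SE = 3.80; t = 7.55/3.80 = 1.99; p about 0.050, just above 0.05 because the interval just includes zero. Using df 60 makes no material difference.
- Gap: 7.55 - 3.48 = 4.07 msec.

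Week 32, MMRM. SE = |estimate| / z, with z from the stated p (normal approximation).
- ITT: -6.06, p = 0.0711; z = 1.805; SE = 3.36; 95% CI about -12.6 to 0.5.
- Per-protocol: -9.13, p = 0.0112; z = 2.536; SE = 3.60; 95% CI about -16.2 to -2.1.
- Gap: 9.13 - 6.06 = 3.07 msec.

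The choice of set changes significance at 0.05 at Week 32 but not at Week 24.

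**What selection of that size would do (assumption only).** Suppose the true effect is zero and a fraction f of the parent gap is selection that persists to the follow-up visit. The rejection rate of the two-sided 0.05 test is P(|Z + f × gap/SE| > 1.96), with SE = SE(per-protocol) × sqrt(82/n).

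| n analysable | gap and SE used | f = 0 | f = 0.5 | f = 1 |
|---|---|---|---|---|
| 82 | 3.07, 3.60 | 5% | 7.1% | 13.7% |
| 82 | 4.07, 3.80 | 5% | 8.3% | 18.8% |
| 41 | 3.07, 3.60 | 5% | 6.0% | 9.3% |
| 41 | 4.07, 3.80 | 5% | 6.7% | 11.8% |

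This scaling treats the per-protocol SEs as if they came from 82 subjects. If the SD is equal in both sets and ITT had 82, the SE ratios imply 82 × (3.36/3.60)² = 71 and 82 × (3.58/3.80)² = 73 per-protocol subjects. Rescaling from 71-73 moves the f = 1 range from 9-19% to about 10-21%.

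**The case against.** The strongest reply is that little is hidden. Every efficacy endpoint is analysed in both sets, so the ITT estimate, interval and p-value will be reported. This is a one-visit follow-up without dosing, stopping rules or multiplicity adjustment, and most secondary endpoints are descriptive, so the label matters mainly for FF-VEP. Per-protocol membership was fixed in the parent study and not tailored to these outcomes. Since version 1.0 already shows the parent results, any choice of set was made knowing them. The gap is untested, comes from nested sets, and may reflect fuller exposure. ITT is itself selected, through return for the visit and the monitor-type rule.

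Much of this stands. The gap is not evidence of bias, the documents show no motive, and the rejection rates are illustrative; they also carry an MMRM standard error over to a single-visit ANCOVA. Counts by treatment group and per-protocol demographics are planned (SAP 3.2.1, 3.2.2, 3.2.4). A justification may lie in redacted text.

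None of it removes the problem. Inherited membership does not explain primary status. The planned accounting gives no reasons for per-protocol exclusion. That ITT carries some selection is no ground for adding an avoidable layer.

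**Conclusion.** The concern holds. The SAP and protocol disagree on the primary efficacy set, no reason is visible, and the SAP's choice conditions on post-randomisation events in a set whose larger BIIB033 effect was already known. This should be corrected before analysis.

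The size of any bias in 215ON203 is unknown: the documents give neither the per-protocol count nor exclusions by arm, and nothing shows whether the parent gap persists at 2-3 years. What can be said is that in the parent study the choice moved the estimate by 4.07 msec at Week 24 and 3.07 msec at Week 32. Inflation of the false-positive rate runs from none, if no part of the gap is selection, to roughly 9-21% under the extreme assumption that all of it is selection and persists.

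**What to change.** - **SAP 3.3.1:** make ITT primary for all efficacy endpoints and per-protocol supportive. State that groups are compared by randomised arm, since the Treatment group paragraph of SAP 3.1 defines them by prior treatment.
- **SAP 3.1 and Protocol 14.1.1:** settle on one definition. The SAP requires at least one assessment and the protocol requires the assessments to be completed, so swapping labels alone would not restore agreement.
- **SAP 3.2.2:** add a table by arm, starting from the 82 dosed subjects, with numbers and reasons for non-return, monitor-type exclusion and each per-protocol criterion.
- **Reporting:** say that ITT as primary removes the per-protocol layer of selection but not that from non-return or the monitor rule.

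If the sponsor keeps per-protocol primary, it must at least justify this and amend the protocol; that would resolve the conflict but not the selection.

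The cost is a swap of roles between two planned analyses, one aligned definition and one disposition table, with no new assessments. The headline estimate may be smaller.

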#### Analysis models

Analysis of covariance (ANCOVA) model will be used as the primary inferential analysis approach to evaluate changes from the baseline measurement in 215ON201 to Day 1 of 215ON203 in efficacy endpoints and to test the treatment differences between BIIB033 and placebo. ANCOVA model will include terms for the baseline value and treatment group. Based on Type III sum of squares, Least-squares (LS) adjusted mean of treatment difference, 95% confidence interval for the difference and the associated p-value will be presented.

Since this is a follow up study, due to loss of follow up, if the distribution of the responses is markedly non-normal (eg., highly skewed or contains outliers), the normality assumption appears dramatically violated, the Wilcoxon rank-sum test will be used to compare the treatment difference of efficacy endpoints. Normal probability plot, and QQ-plot with tests will be used to check normality assumption.

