14.1.2.1. Analysis of the Primary Endpoint

The primary analysis will be on the change in FF-VEP latency of the affected eye as compared to the baseline (measured prior to dosing in Study 215ON201) of the fellow eye at 2 years (+ up to 12 months) after the last study visit assessment (Week 32 or the projected Week 32 visit) in Study 215ON201. The ANCOVA model will be used to test the difference between the 2 original treatment groups from Study 215ON201, adjusting for the baseline of the unaffected fellow eye.

[figure not shown]

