### 3 STATISTICAL ANALYSIS METHODS

#### 3.1 General Considerations

Descriptive summary statistics will be presented for all study primary, secondary and [REDACTED] endpoints collected.

Unless stated otherwise, summary statistics will be presented by original treatment groups and overall. For continuous endpoints, the summary statistics will generally include number of subjects enrolled, number of subjects evaluated, mean, standard deviation, median, and range (minimum, maximum). For categorical endpoints, the summary statistics will generally include number of subjects enrolled, number of subjects evaluated, and the percent of subjects in each category.

Statistical testing for efficacy endpoints will be made between the BIIB033 group and the placebo group. There will be no multiple comparison adjustments.

Unless stated otherwise, all statistical tests will be 2-sided with statistical significance level of 0.05.

The statistical software, SAS®, will be used for all summaries and statistical analyses.

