### **Latency as determined by FF-VEP**

P100 latency value from FF-VEP is the primary efficacy outcome and will be measured for affected and fellow eyes at Day 1.

The actual value for affected eye, fellow eye and the difference between the two eyes at Day 1 will be summarized using descriptive statistics by treatment group.

Change in latency value at Day 1 for the affected eye in the current study from the baseline of fellow eye in RENEW will be analyzed using ANCOVA as mentioned in Section 3.3.1. The baseline of the fellow eye in RENEW will be used as the baseline covariate in above ANCOVA model.

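### SAP 3.3.1 lets the primary ANCOVA be replaced by a Wilcoxon test without the fellow-eye covariate, on a trigger with no visible cut-off or decision time

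*SAP*

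**What the plan says.** Protocol 14.1.2.1 names one primary test and no alternative: "The ANCOVA model will be used to test the difference between the 2 original treatment groups from Study 215ON201", adjusted for the fellow eye's baseline.

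SAP 3.3.1 (Analysis models) starts from the same place: "ANCOVA model will include terms for the baseline value and treatment group". It then adds a fallback. The trigger is "if the distribution of the responses is markedly non-normal (eg., highly skewed or contains outliers", and the text goes on that, where "the normality assumption appears dramatically violated, the Wilcoxon rank-sum test will be used to compare the treatment difference of efficacy endpoints". The tools are given as "Normal probability plot, and QQ-plot with tests will be used to check normality assumption".

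SAP 3.3.2 says the change in latency "will be analyzed using ANCOVA as mentioned in Section 3.3.1", with the fellow-eye baseline as covariate. The fallback therefore covers the primary endpoint. SAP 3.1 sets the standard: "all statistical tests will be 2-sided with statistical significance level of 0.05", and "There will be no multiple comparison adjustments".

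The visible text names no normality test, cut-off or decision time, does not say who decides, and does not say whether treatment codes may be attached when the check is made. SAP Appendix 1 is headed as example SAS code for Sections 3.3.1 and 3.3.3, but its content is not shown, so these statements apply to the visible text only.

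**The concern.** A primary test should be fixed before the data can influence it. Here the words that decide between two tests are matters of judgement, and the outlier example could be met by a single eye. Three features add to this.

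- The trigger refers to the responses. ANCOVA assumes normal residuals, and the two can look different when a covariate or a treatment effect is present.
- The Wilcoxon rank-sum test drops the fellow-eye covariate that both documents specify for the primary analysis. It also tests a different hypothesis from a difference in means.
- The rule does not say whether the decision is taken once, or separately for the per-protocol and ITT populations and for the interim and final analyses. SAP Section 4 includes the FF-VEP latency analysis at the interim.

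The choice could matter. In the parent study the per-protocol ANCOVA at Week 24 was -7.55 msec (95% CI -15.12 to 0.01; Protocol 5.6), which is almost exactly on the 0.05 boundary. A result of that kind in the follow-up could fall on either side depending on the test.

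**Working it through.** The documents give no sample-size calculation, so there is no design figure to reproduce. The only operating figure is the two-sided 0.05 level. The question is what the switch does to it.

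**Residual SD, from Protocol 5.6.** SE = CI half-width / t, and SD = SE × √(n/2), with n per arm.

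- ITT, Week 24: half-width (3.65 + 10.61)/2 = 7.13. With 41 per arm, SE = 3.58 and SD = 3.58 × √20.5 ≈ 16.2. With 36 per arm, SD ≈ 15.2.
- Per-protocol, Week 24: half-width (0.01 + 15.12)/2 = 7.565, so SE ≈ 3.8. SD is 17.2 with 41 per arm and 14.6 with 30. The implied p is about 0.0503.

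An SD of 16 msec was used.

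**Assumptions not in the documents.** 26 per arm (41 is the maximum); fellow-eye baseline SD 6 msec; slope of the change on that baseline 0 or -1; errors normal, skewed (lognormal), or with 10% outliers. There were 8,000 runs per null scenario (Monte Carlo SE about 0.25 points) and 4,000 per alternative. The mechanical switch was Shapiro-Wilk p < 0.05.

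**Type I error, ranges over both arm sizes and both slopes:**

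| Errors | ANCOVA always | Wilcoxon always | Mechanical switch, responses | Mechanical switch, residuals | Smaller of the two p-values |
|---|---|---|---|---|---|
| Normal | 4.9–5.2% | 4.6–4.9% | 5.0–5.2% | 5.1–5.3% | 5.8–7.0% |
| Skewed | 4.3–4.4% | 4.7–5.0% | 4.6–5.0% | 4.7–5.1% | 6.8–7.3% |
| Outliers | 4.4–4.9% | 4.6–5.2% | 4.7–5.1% | 4.9–5.3% | 6.4–7.7% |

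Switching by a fixed rule is harmless to the level. Unrestricted choice adds about 1 to 3 points.

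**Power with a 9.13 msec effect (parent per-protocol Week 32 estimate), 26 per arm:**

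| Errors, slope | ANCOVA | Wilcoxon | Wilcoxon minus ANCOVA | Tests disagree at 0.05 |
|---|---|---|---|---|
| Normal, 0 | 52.3% | 49.9% | -2.4 | 8.7% |
| Normal, -1 | 50.5% | 44.1% | -6.4 | 14.7% |
| Skewed, 0 | 60.4% | 89.9% | +29.5 | 30.0% |
| Skewed, -1 | 58.7% | 74.7% | +16.0 | 24.3% |
| Outliers, 0 | 55.6% | 75.7% | +20.1 | 23.1% |
| Outliers, -1 | 56.7% | 64.7% | +8.0 | 21.9% |

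Disagreement is 9% to 24% in five of the six scenarios and 30% in the sixth. Runs under other assumed settings put it at about 8% to 24%.

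**What losing the covariate costs.** The share of variance it explains is (slope × baseline SD)² / [(slope × baseline SD)² + residual variance]. At slope -1 and SD 6 this is 36/(36 + 256) = 12%. At slope -0.3 and SD 7, with residual SD 16.2, it is 4.41/(4.41 + 262.4), or about 2%. The power loss with normal errors follows: about 6 points in the first case and 1 to 3 in the second.

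**A rank analysis that keeps the covariate.** In simulation, ANCOVA on ranks held type I error at about 4% to 5.5% and had 0 to 11 points more power than Wilcoxon.

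**The case against.** The strongest reply is that the SAP writes a conditional replacement. A reader might infer that the plan gives two chances at significance, but nothing in the text allows both tests to be run and the smaller p-value kept. This stands. The 6% to 8% figure describes discretion that the wording fails to exclude, not the rule as written. If free choice is confined to data that fail Shapiro-Wilk on the responses, type I error is 4.9% to 5.5% with normal errors and 6.0% to 6.7% with skewed or heavy-tailed ones.

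Other stronger readings also fail.

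- *The msec estimate disappears after a switch.* SAP 3.3.1 says the LS mean difference, its interval and p-value will be presented, without condition. Nothing says they are withheld.
- *The choice is made on unblinded data.* Protocol 9.3 withholds codes from sites and patients and is silent on the sponsor's analysts. The documents do not say when normality is checked or by whom. The gap is the missing requirement, not evidence of unblinded selection.
- *Checking responses distorts the level.* The two mechanical checks give nearly the same error rate. The reference to responses is imprecise, and the closing sentence on checking the assumption names no quantity.
- *The fallback ignores the fellow eye.* The endpoint is still a change from the fellow-eye baseline. Only the covariate adjustment is lost.
- *A rank test is offered as a cure for loss to follow-up.* The clause is unclear and may only mean that attrition leaves a small sample in which normality matters more.

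It is also true that Wilcoxon is the more powerful test under skewed or outlier-prone errors, so a robust method has a real place.

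**Conclusion.** The point holds as a gap in pre-specification. The SAP allows the protocol's covariate-adjusted primary test to be replaced by a rank test without the covariate, and the visible text fixes neither the threshold nor the timing. The consequence is modest: about 5% type I error under any mechanical rule, and at most about 6% to 8% if the choice followed sight of both results. The practical exposure is a borderline result, since the two tests would disagree in roughly 8% to 24% of trials with a 9.13 msec effect, and in 30% of the most skewed scenario. The residual SD comes from the parent intervals. Arm size, baseline SD, slope and error shape are assumptions, and the disagreement figure is sensitive to error shape. Appendix 1 could narrow the point if its code fixes the normality test.

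**What to change.** Change the wording of SAP 3.3.1:

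1. Name ANCOVA adjusted for the fellow-eye baseline as the single primary test, as in the protocol, and always report its LS mean difference and confidence interval in msec.
2. Replace the Wilcoxon fallback with one pre-specified rank analysis that keeps the covariate, for example ANCOVA on ranks, always reported as a sensitivity analysis.
3. Check residuals, not responses, and use the check for interpretation.

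If the sponsor prefers to keep a switch, state a numeric residual-based rule, apply it before treatment codes are linked, make rank ANCOVA the fallback, and add the fallback to the protocol.

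The work is wording only. The statistical cost is real: with strongly skewed or heavy-tailed errors, fixed ANCOVA gives up about 10 to 25 points of power relative to a rank test (8 to 29.5 in the four non-normal rows above). The rank result stays visible as the sensitivity analysis. The numeric-switch option keeps most of that power at about 5% type I error, at the price of a less simple primary analysis.
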